## **8.10 Interim Analysis**

Two partially unblinded interim analyses (IA) are planned for this study. To protect study integrity, the IA will be performed by an independent statistician and statistical reporting group who are not involved in the clinical trial conduct and are not responsible for the final analysis of clinical trial data. Each interim analysis will be governed by a separate interim analysis charter.

### **8.10.1 Interim Analysis 1 (IA1)**

The first interim analysis will be conducted when approximately 75 subjects have completed the week 12 visit to review safety, tolerability. The key secondary endpoints in IA1 will be noninvasive tests (NITs): MRI-PDFF, MRE and non-invasive fibrosis markers. No analysis of the primary endpoint will be performed in IA1. PK, PD and PK/PD endpoints will be summarized as described in Section 8.8.

The results to be submitted in IA1 will include all the displays for safety endpoints: treatment compliance, AEs, lab, ECG, vital signs, concomitant medications and physical examination; disposition and demographics results; and results for key secondary endpoints: MRI-PDFF, MRE and non-invasive fibrosis markers.

Analysis for the liver MRI-PDFF, liver MRE and non-invasive markers is provided in [Section 8.6.3.2.2](#), [Section 8.6.3.2.3](#) and [Section 8.6.4.1](#) respectively.

### **8.10.2 Interim Analysis 2 (IA2)**

The second interim analysis when approximately 35-40% of subjects have completed the week 72 biopsy. The analysis for the primary endpoint will be performed in IA2. A Lan-Demets alpha spending function with O'Brien-Fleming boundaries will be applied to control type I error at 0.025 significance level (two-sided) for each primary endpoint. Adjusted alpha obtained with this method will be used in second interim analysis.

Each primary endpoint will be analysis using the logistic regression model given in [Section 8.6.2](#). A step-down sequential testing procedure will be used to control multiplicity in testing each dose vs placebo.

PK, PD and PKPD endpoints will be summarized as described in Section 8.8.

### **8.11 COVID-19 Impact on Study**

Additional analysis will be performed to recognize and indicate the impact of participation of subjects by COVID-19. The impact of COVID-19 will be summarized by treatment group and overall by visit for all screened subjects. This table will present the subjects affected by COVID-19 in all aspects (e.g., missed visit and/or assessment due to COVID-19, remote visit due to COVID-19, modified assessment due COVID-19). In addition important protocol deviations related to COVID-19 using randomized subjects will be summarized.

A by-subject listing will also be provided for all subjects that have their participation impacted by COVID-19.

## Final Analysis Statistical Analysis Plan (SAP)

### 9 CHANGES TO PLANNED ANALYSIS FROM STUDY PROTOCOL

This study was terminated by Enanta on October 4th, 2021. At the time the study was terminated no subject had completed Week 72 study assessments. Any analyses planned through week 72 will present all data collected through study termination, and only summary statistics will be provided post Week 12 visit. Any analyses at week 72 will not be performed.

Consequently, the following analyses will not be performed,

SAP Section	Analysis: Endpoint(s)
8.6.2	Primary Efficacy: All
8.2.6.1	Sensitivity Analyses for Primary Endpoints: All
8.6.3.1	Secondary Efficacy Analysis: Categorical Endpoints (Responder at Week 72) – All
8.6.2.3.4	Secondary Efficacy Analysis: Continuous Endpoint Adiponectin through week 72
8.6.4.2	Exploratory Analysis at Week 72: NAFLD Fibrosis Score, AST to Platelet Ratio Index
8.6.4.3	Exploratory Analysis at Week 72: CRP, IL-6, IL-1 $\beta$ , TNF- $\alpha$ , TNF- $\beta$ , alpha2 macroglobulin and haptoglobin levels
8.6.4.5	Exploratory Analysis: ASCVD Score
8.8	Pharmacokinetics (PK) and Pharmacokinetics/Pharmacodynamics (PK/PD) Analysis: All Analyses with the following exceptions: 
 
• Summary of AUC0-8 and AUC2-8 for C4, change from baseline and percentage change from baseline at Week 12 for subjects with and without pruritus
 
• Scatterplot of FGF19 concentrations at Week 12 vs FGF19 Week 12 Change from Baseline value
 
• Scatterplot of C4 concentrations at Week 12 vs C4 Week 12 Change from Baseline value
 
• Scatterplot of Bile Acid concentrations at Week 12 vs Bile Acid Week 12 Change from Baseline value
 
• Boxplot of predose concentration at Weeks 2, 4, 8, and 12 for EDP-305 and EP-022679 by treatment group for subjects with and without pruritus
 
• Listing of EDP-305 & EP-022679 concentrations for subjects with pruritus
 

8.9	Subgroup Analyses: All
8.10.2	Interim Analysis #2: All
8.11	Analysis of COVID-19 Impact on Study: All

- The following listings have been added: Informed Consent and Rescreening data will be listed for all enrolled subjects.
- Inclusion and exclusion criteria will be listed for all enrolled subjects.

## 11 APPENDICES

### Appendix A – Statistical Model

#### SAS code for Logistic regression analysis

```
PROC GENMOD data=dataset ;  
  class trt01pn(ref=0) diab_st vitE_pio;  
  freq count;  
  model Resp = trt01pn diab_st vitE_pio baseline_NAS / alpha=0.xx dist=binomial  
  link=logit ;  
  lsmeans trt01pn/ CL pdiff exp;  
  ods output lsmeans = lsmeans1  
             diffs=diffs1;
```

**RUN;**

Note:

1. Use data without any imputation.
2. Resp: Responder (Yes/No)
3. diab\_st: Baseline diabetes status
4. vitE\_pio: Use of Vitamin E and/or pioglitazone
5. Baseline\_NAS: Baseline value of NAS
6. 0.xx=level of significance to be used
7. Use numeric variables for treatment group
8. Code **trt01pn** as Placebo=0, EDP 305 2 mg=1, EDP 305 1.5 mg=2

For Primary analysis: The EDP-305 2 mg will be compared to placebo using a two-sided alpha of 0.0xx (adjusted alpha/2 ) first then if the difference is statistically significant, EDP-305 1.5 mg will be compared to placebo using a two-sided alpha of 0.0xx (adjusted alpha/2).

#### SAS code for Fisher Exact Test

```
ods output fishersexact=fishers;
```

```
PROC FREQ data=dataset;
```

```
tables trt01pn*responder /exact out=count;
```

**RUN;**

Note:

1. Use data without any imputation
2. Fishers: Output dataset for Fisher's Exact test (for p-value)

## Final Analysis Statistical Analysis Plan (SAP)

### SAS code for ANCOVA analysis

```
PROC MIXED data = dataset method=type3;  
  class trt01pn(ref=0) diab_st vitE_pio;  
  model CHG = trt01pn diab_st vitE_pio baseline_NAS baseline_parameter /ddfm=KR;  
  lsmeans trt01pn /pdiff ;  
  ods output    LSMEANS=lsm  
                DIFFS=diff ;  
RUN;
```

### Note:

1. Use data without any imputation.
2. CHG: Change from baseline.
3. diab\_st: Baseline diabetes status
4. vitE\_pio: Use of Vitamin E and/or pioglitazone
5. Baseline\_NAS: Baseline value of NAS
6. Baseline\_parameter: Baseline value of the parameter to be analysed.
7. Use numeric variables for treatment group
8. Code **trt01pn** as Placebo=0, EDP 305 2 mg=1, EDP 305 1.5 mg=2

### SAS code for MMRM analysis

```
PROC MIXED data = dataset method=type3;  
  class trt01pn(ref=0) visitn usubjid ;  
  model CHG = trt01pn visitn trt01pn*visitn baseline_NAS baseline_parameter  
  /ddfm=KR;  
  repeated trt01pn / type = UN subject = usubjid;  
  lsmeans trt01pn*avisitn /pdiff ;  
  ods output    LSMEANS=lsm  
                DIFFS=diff  
RUN;
```

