#### **11.6.1. Secondary Efficacy Analysis**

Secondary endpoints will be analyzed for treatment group differences. Multiple sensitivity analyses will be performed on the primary efficacy endpoints.

For categorical endpoints (e.g., proportions) a logistic regression model testing between treatment differences with terms for diabetes status and use of Vitamin E and/or pioglitazone and baseline covariate NAS included in the model. Odds ratio and the 95% confidence intervals will be reported. If convergence is encountered the Fisher's exact test will be used to test treatment group differences.

For continuous endpoints (e.g., change from baseline) an analysis of covariance (ANCOVA) model testing treatment differences with terms for baseline diabetes status and use of Vitamin E and/or pioglitazone, baseline covariate NAS, and baseline parameter of interest included in the model. A type III sum-of-squares for the least-squares means and 95% confidence intervals will be reported.

When continuous endpoints that are repeated over visits a restricted maximum likelihood-based mixed model repeated measures (MMRM) technique may be performed. The model will include treatment, baseline covariate NAS, baseline parameter, visit, treatment-by-visit interaction as fixed effects. An unstructured variance-covariance structure will be considered to model the within-patient error. If the unstructured covariance matrix results in a lack of convergence, the heterogeneous Toeplitz covariance structure should be used. The Kenward-Roger method will be used to estimate the denominator degrees of freedom. A type III sum-of-squares for the least-squares means and 95% confidence intervals will be reported.

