#### **Mixed Model Repeated Measures (MMRM) analysis**

A MMRM analysis will be performed for secondary efficacy endpoints that are continuous in nature and assessed over multiple study visits. The SAS procedure PROC MIXED will be used. The preferred model will include the fixed categorical effects of treatment group, visit, treatment-by-visit interaction as well as the continuous fixed covariates of baseline measurement for the parameter of interest and baseline NAS score. An unstructured variance-covariance structure will be considered to model the within-patient error. If the unstructured covariance matrix results in a lack of convergence, the heterogeneous Toeplitz covariance structure should be used. The Kenward-Roger method will be used to estimate the denominator degrees of freedom. A sample of SAS code for MMRM is provided in [Appendix A](#).

The model will provide least-squares means (using type III sum-of-squares), standard errors, p-value and 2-sided 95% confidence interval for treatment differences for each visit.

[figure not shown]

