#### **8.6.3.2.1 Change from baseline in 5D-itch scale and Visual Analog Score (VAS) through week 72**

Pruritus will be monitored in this study at day 1, 7, weeks 2, 4, 8, 12, 16, 20, 24, 28, 32, 36, 40, 44, 48, 56, 64, 72 and EOS.

Observed values, change from baseline, and percentage change from baseline for VAS scores and each dimension of 5D-itch scale and overall score will be summarized using an 8-number summary by visit and treatment group.

Change from baseline for VAS and 5D-itch scale will be analyzed using a restricted maximum likelihood-based mixed model repeated measures (MMRM) technique. The model will include treatment, visit, treatment-by-visit interaction as fixed effects along with baseline NAS score and baseline score for VAS and 5D-itch scale as covariate respectively. Variance-covariance structure to be used to model the within-patient error and results to be presented are described in [Section 8.6.1](#). The details for calculation of score is given in [Appendix B](#).

A by-subject listing will be provided for observed and derived variables for VAS and 5D-itch scale.

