### Note:

1. Use data without any imputation.
2. CHG: Change from baseline.
3. Baseline\_NAS: Baseline value of NAS
4. Baseline\_parameter: Baseline value of the parameter to be analysed.
5. Use numeric variables for visits and treatment group
6. Code **trt01pn** as Placebo=0, EDP 305 2 mg=1, EDP 305 1.5 mg=2
7. If model does not converge then use type=TOEPH

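### The sample MMRM code in SAP Appendix A makes treatment the repeated effect, so as printed it cannot give the per-visit results the SAP text promises

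*SAP*

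**What the plan says.** **The text.** SAP 8.6.1 describes an MMRM with treatment, visit, treatment-by-visit interaction, baseline value and baseline NAS. On the covariance it says: "An unstructured variance-covariance structure will be considered to model the within-patient error". Heterogeneous Toeplitz is the fallback. The output is to include a "2-sided 95% confidence interval for treatment differences for each visit". SAP 8.6.3.2.1 (VAS, 5D-itch) says the analysis is done "using a restricted maximum likelihood-based mixed model repeated measures (MMRM) technique"; SAP 8.6.3.2.4 (lipids, adiponectin) and protocol 11.6.1 also specify REML.

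**The code.** The MMRM block in Appendix A:
- sets `method=type3`;
- puts `visitn` in CLASS and MODEL;
- specifies "repeated trt01pn / type = UN subject = usubjid";
- requests "lsmeans trt01pn*avisitn /pdiff".

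Its note 7 adds: "If model does not converge then use type=TOEPH". The logistic sample, by contrast, requests limits: "lsmeans trt01pn/ CL pdiff exp".

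**The strata.** SAP 3.4 stratifies randomisation by diabetes status and by Vitamin E/pioglitazone use. The logistic and ANCOVA models in SAP 8.6.1 include both factors; the MMRM includes neither. That follows the protocol: "The model will include treatment, baseline covariate NAS, baseline parameter, visit, treatment-by-visit interaction as fixed effects".

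**The concern.** In a REPEATED statement, the named effect tells the software which row and column of the covariance matrix each record belongs to. For repeated visits that effect has to be visit. Here it is treatment, which in a parallel-group trial takes one value per subject. The code therefore models no covariance between visits, although that is what the unstructured matrix is for.

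Three smaller faults sit in the same block: the estimation method conflicts with the text, LSMEANS names a visit variable used nowhere else in the block, and no confidence limits are requested.

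At stake are the inferential results for pruritus and lipids that survive the study's termination. Pruritus is a stated secondary objective, and the protocol's dose rationale (4.2.2) turns partly on it.

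**Working it through.** The documents give no numerical figure to reproduce. The check is algebra plus a comparison of text with code; the code was not run in SAS.

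**1. Covariance as coded.** For subject *i* with *m* records, R_i[j,k] = G[level_j, level_k], where level is the value of the repeated effect.
- Repeated effect = treatment. Every record of a subject in arm *t* has level *t*, so each entry of R_i is σ_t² and R_i = σ_t² × (*m* × *m* matrix of ones). Its rank is 1, and its determinant is 0 for every *m* ≥ 2.
- For *m* = 1, R_i = σ_t², which is not singular.
- TOEPH over treatments changes only the off-diagonal terms of G, which no subject uses. R_i is the same matrix.
- Numerical check: *m* = 2, 3, 4, 5, each of three arms, UN and TOEPH, gives 4 × 3 × 2 = 24 cases. All have rank 1 and determinant 0.
- Repeated effect = visit. UN has full rank: 4 of 4 for lipids and 5 of 5 for the itch scales up to Week 12.

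**2. Covariance parameters up to Week 12.**

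| Repeated effect | Levels | UN, k(k+1)/2 | TOEPH, 2k−1 |
|---|---|---|---|
| Visit, lipids (Weeks 2, 4, 8, 12) | 4 | 10 | 7 |
| Visit, itch (Day 7 and the same weeks) | 5 | 15 | 9 |
| Treatment, as coded | 3 | 6 | 5 |

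As coded, only the three arm variances enter any R_i. The other 3 (UN) or 2 (TOEPH) parameters are informed by no subject.

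**3. Text against code.**

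| Item | Text | Code |
|---|---|---|
| Estimation | REML (SAP 8.6.3.2.1, 8.6.3.2.4; protocol 11.6.1) | `method=type3` |
| Visit | no variable named | `visitn` in CLASS and MODEL, `avisitn` in LSMEANS |
| MMRM limits | 95% CI at each visit (SAP 8.6.1) | no `cl` |
| ANCOVA limits | 95% CI (SAP 8.6.1) | no `cl` |

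The visit mismatch lies inside the block rather than between block and text. SAP 8.6.1 and protocol 11.6.1 mention type III sums of squares for the LS-means, which probably explains `method=type3`. It does not justify the option, because `method=` sets how the model is estimated. The ANCOVA sample carries the same option, but its text does not call for REML, so there is no such conflict there.

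**4. Reach.** SAP Section 9 cancels the Week 72 analyses and adiponectin, and limits results after Week 12 to summary statistics. It does not list the models for VAS, 5D-itch, TG, TC, HDL-C or LDL-C up to Week 12. The maximum number of differences is 2 doses × (4 lipids × 4 visits + 2 itch scales × 5 visits) = 2 × 26 = 52.

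**5. The strata.** The documents give neither the share of residual variance the strata explain (R²) nor the number of subjects in the surviving models. Assume R² of 0% to 10%, and n from 30 (assumed) to 336 (planned enrolment, protocol Section 3). In a single-visit approximation there are 5 mean parameters without the strata and 7 with them.
- Interval width without/with strata = [1/√(1−R²)] × t(n−5)/t(n−7), with t at 0.975.
- The two degrees of freedom cost 0.44% at n = 30 and 0.002% at n = 336.

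| R² | Ratio, n = 30 | Ratio, n = 336 | Effect of adding strata |
|---|---|---|---|
| 0% | 0.9956 | 1.0000 | 0.4% wider to no change |
| 2% | 1.0057 | 1.0101 | 0.6% to 1.0% narrower |
| 5% | 1.0215 | 1.0260 | 2.1% to 2.5% narrower |
| 10% | 1.0494 | 1.0541 | 4.7% to 5.1% narrower |

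The last column is 1 minus the reciprocal of the ratio. Break-even R² = 1 − [t(n−5)/t(n−7)]⁻² when the ratio is written as t(n−7)/t(n−5): 0.88% at n = 30 and 0.004% at n = 336.

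**The case against.** The strongest reply is that the text governs. The SAP labels the block a sample, and 8.6.1 with its subsections states visit effects, within-patient covariance, REML and per-visit intervals. A competent programmer would follow the text, and the printed code would fail openly: a singular matrix cannot be inverted, and the LS-means are requested for an effect the model lacks. This stands and sets the severity. It does not remove the point. The block is the SAP's only worked specification of this model, and note 7 sends the programmer to a fallback that cannot help.

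The count of 52 can also be challenged, fairly. Section 9 never says the MMRM will be refitted to data up to Week 12; that is inferred from its absence from the cancelled list. Protocol 8.3.5 gives the 5D-itch only when VAS is above zero, so its change from baseline may be sparse. Hence 52 is a maximum.

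On the strata, leaving them out follows the protocol and causes no bias. A reader might infer that the SAP contradicts its own randomisation scheme; it does not. The gain rests on an R² that the documents do not give.

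The absent semicolon after `DIFFS=diff` may come from reading the PDF and is not counted.

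**Conclusion.** The MMRM code is wrong as written. For every subject with two or more post-baseline records it specifies a rank 1 covariance, under UN and under TOEPH. It also conflicts with the stated REML estimation, is inconsistent in its visit variable, and omits promised confidence limits, as does the ANCOVA sample.

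Severity is minor. A reader might infer that the planned model is unsound, or that biased estimates could go unnoticed. The documents do not support either: the text describes a sound model and the failure would be visible. No primary or multiplicity-controlled test uses this block. The exposure is at most 52 differences up to Week 12, assuming those models are still run.

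Adding the strata is a separate, optional improvement. It would narrow intervals by about 1% to 5% at assumed R² of 2% to 10%, with essentially no gain at zero.

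**What to change.** **Correct Appendix A.** In the MMRM block:
- replace `method=type3` with `method=reml`;
- use `repeated visitn / type=UN subject=usubjid;`
- use `lsmeans trt01pn*visitn / pdiff cl;`

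Note 7 can stay, since TOEPH works once visit is the repeated effect. In the ANCOVA block, add `cl` to the LSMEANS line. These edits bring the samples into line with the existing text, change no planned method and cost nothing.

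**Optional.** Add `diab_st` and `vitE_pio` to the MMRM in SAP 8.6.1, 8.6.3.2.1, 8.6.3.2.4 and Appendix A. This costs two model degrees of freedom and a written justification, because it departs from protocol 11.6.1. Protocol 11.1 allows changes in the SAP only before unblinding. SAP 1.0 postdates the termination, and the documents do not say whether the blind still held. If it did, justify the change in the SAP; if not, in the clinical study report.

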### Note:

1. Use data without any imputation.
2. CHG: Change from baseline.
3. Baseline\_NAS: Baseline value of NAS
4. Baseline\_parameter: Baseline value of the parameter to be analysed.
5. Use numeric variables for visits and treatment group
6. Code **trt01pn** as Placebo=0, EDP 305 2 mg=1, EDP 305 1.5 mg=2
7. If model does not converge then use type=TOEPH

## Appendix B – Scoring for Scales

### 5D-itch scale

5D-itch scale is developed by Elman (Elman, Hynan, Gabriel, & Mayo, 2010) and will be used to assess pruritus in subjects. The five dimensions (aka domains) assessed in 5D-itch scale are duration, degree, direction, disability, and distribution.

The disability domain will be the highest score obtained from the daily activities of sleep, leisure/social activities, housework/errands, and work/school. The disability domain will only be calculated if at least 3 daily activities are documented.

The distribution domain includes 16 locations of itch and is categorized to a scale of 0 to 5, based on the sum of the number of affected locations: sum of 0 to 2 = score of 1, sum of 3 to 5 = score of 2, sum of 6 to 10 = score of 3, sum of 11 to 13 = score of 4, sum of 14 to 16 = score of 5.

The total 5D score is obtained by summing up the five domain scores and ranges between 5 (no pruritus) and 25 (most severe pruritus). The total score will not be calculated if any of the domain scores is missing.

### Quality of Life scales - CLDQ-NASH

CLDQ-NASH scale includes 36 items grouped into 6 domains: Abdominal Symptoms, Activity/Energy, Emotional Health, Fatigue, Systemic Symptoms, and Worry. This questionnaire is designed to find out how a subject had been feeling during the last two weeks. Subject will be asked about their symptoms related to their fatty liver disease, how they have been affected in doing activities, and how their mood have been.

In CLDQ-NASH, patients are asked about how frequently they experience certain problems or how they have been affected in doing activities impairing various aspects of their well-being; a 1-7 Likert scale is used for the responses such that the score of 1 corresponds to a problem is experienced “All of the time”, and the score of 7 to “None of the time”.

The scores will be calculated separately for each domain as an average of the domain’s items. In all domains, greater scores reflect better health. The total CLDQ-NASH score will be obtained as the average of the domain scores.

### Cardiovascular risk score (ASCVD)

## Final Analysis Statistical Analysis Plan (SAP)

### Data Derivation Details to Obtain Scale Scores for SF-36

SF-36 questionnaire includes 8 domains with 36 items. This questionnaire designed to get idea about the subjects views about his/her health and to track of how the subject is feeling and if subject is able to do your usual activities.

	DERIVATION
SF-36 PF scale score	
raw score = sum (items 3A, 3B, 3C, 3D, 3E, 3F, 3G, 3H, 3I, 3J)
 
<math>PF = [(raw\ score - 10) / 20] * 100</math>
 
<math>PF\_Z = (PF - 83.29094) / 23.75883</math>
 
<math>PF\ scale\ score = (PF\_Z * 10) + 50</math>
 
When calculating the raw score, if 5 or more of the items are non-missing then replace any missing values as follows:
 
Calculate the mean of the answered questions, using the number of answered questions as the denominator. Substitute the mean for any missing scores.
 
Otherwise, if less than 5 of the items are non-missing then PF scale score is missing.
 
The response scale for each activity ranges from 1 to 3 where 1=limited a lot, 2=limited a little, and 3=not limited at all. A higher PF scale score indicates better physical functioning.

